5.1.2. Packaging and Labeling

The Sponsor will be responsible for ensuring that the treatment is manufactured in accordance with applicable Good Manufacturing Practice regulations and requirements. All labels for study drugs will meet applicable requirements of the protocol and the Canadian Health Products and the US Food and Drug Administration (FDA).

5.1.3. Storage and Handling

Lasmiditan tablets should be stored by the study site at controlled room temperature of 25°C (77°F); excursions are permitted to +/- 15°C (59°F-104°F).

5.2. Method of Assigning Subjects to Treatment Groups

No randomization will be performed for this study. Instead subjects will be categorized into either the control group of healthy volunteers with normal hepatic function, or into one of the two groups of subjects with varying degrees of hepatic impairment (mild or moderate hepatic impairment).

Once a subject number has been assigned to a subject, it will not be reassigned to another subject. Subjects who withdraw from the study may be replaced. Replacement subjects will not be enrolled for subjects who discontinue the study due to treatment-related toxicity. A new unique subject number will be assigned to the replacement subject.

5.3. Blinding

No unblinding procedure is required, as this is an open-label study.

5.4. Dosing and Administration

5.4.1. Dispensing

Designated site staff will dispense study drug in tablet form.

Study drugs will be administered to the subjects under supervision of the study center personnel.

5.4.2. Administration Instructions

The study drug will be administered orally in the morning.

Dosing will be performed by trained personnel and supervised by the Principal Investigator or physician in charge.

Subjects will be asked to fast overnight (no food or drink, except water) prior to dosing, for a minimum of 10 hours, at Day -1. Fasting will continue for at least 4 hours following drug administration, after which a standardized lunch will be served. A supper, a light snack and other meals will also be served at appropriate times thereafter, but not before 9 hours after dosing.

Fluid intake other than water will be controlled during the housing period and for all subjects. Water will be provided *ad libitum* until 1 hour pre-dose. The drug will be given with about 240 mL (8 oz.) of water at room temperature. Water will be allowed *ad libitum* beginning 1 hour after the administration of the drug.

The tablet must be swallowed whole and must not be chewed or broken.

Study medications will be administered to each subject consecutively, and at adequate intervals, for the purpose of accurate sampling time. The date and time of each dose must be recorded.

The physician in charge will remain at the clinical site for at least the first 4 hours following drug administration, and will remain available at all times during the study.

5.4.3. Treatment Compliance

The following measures will be employed to ensure treatment compliance:

- All doses will be administered under the supervision of the Investigator (or designee).
- A mouth and hand check of all subjects will be carried out to ensure that all tablets have been swallowed.

5.4.4. Study Drug Accountability

Complete and accurate records of all study drugs must be kept. This includes acknowledgment of receipt of each shipment of study product (quantity and condition), subject dispensing records, and returned or destroyed study product.

At the conclusion of the study, all unused investigational products and all medication containers will be returned to the Sponsor unless the Sponsor has approved other arrangements. Drug accountability will be performed at the completion of the trial.

5.5. Prior and Concomitant Medication

Hepatic-impaired subjects will be permitted to continue taking any prescription or OTC medication necessary for the management of their hepatic disease or other concurrent illness. The dosing schedules for such medications must be stable for 2 weeks before day 1 of the study (except for insulin) and maintained throughout the study. Minor dose changes consistent with treatment practices may be permitted at the discretion of the Investigator. All medications taken during the 14 days prior to dosing will be recorded in the subject's CRF and reviewed by the Investigator. When concomitant medications are administered, the indication, name, dose, route, and frequency will be recorded in each subject's CRF.

For healthy subjects, beside enzyme-modifying drugs that are not allowed for 28 days (refer to exclusion criteria), subjects will be requested to abstain from taking any prescription medications used with the intention to treat a condition for 28 days prior to dosing and during the study, unless judged differently by the Principal Investigator or designee. Systemic contraceptives and hormone replacement therapy will be permitted. Subjects will also be requested to abstain from taking any over-the-counter (OTC) products for 7 days prior to dosing and during the study. They will be specifically reminded that this includes cold preparations (containing ASA), acetylsalicylic acid (ASA), vitamins and natural products used for therapeutic benefits and antacid preparations. Vitamins used as nutritional supplements in non-therapeutic doses (as judged by the Principal Investigator or designee) may be accepted, but they must be stopped at least 48 hours prior to dosing and during the study.

If a medication (including OTC) other than those specified in the protocol is used after dosing or at any time before the end of the study, the Principal Investigator or designee and/or the Sponsor will decide whether the subject will be permitted to remain in the study, depending on the drug used, the time of drug intake, etc. The drug and dose will be noted.

5.6. Study-Specific Restrictions

- Subjects will be requested to abstain from alcohol for 48 hours prior to dosing and during the study period. Throughout the study (including the return visits), in case of any doubt about alcohol consumption, a test for alcohol may be performed to confirm the physician's judgment.
- During the study, subjects who are light-smokers should not smoke more than 10 cigarettes per day. They will also be instructed to abstain from smoking for 2 hours prior to and until 4 hours after drug administration.
- Subjects will be requested to avoid food or beverages containing xanthines (i.e. tea, coffee, cola drinks, energy drinks or chocolate) for 48 hours prior to dosing and during study period.
- Subjects will be instructed to avoid food or beverages containing grapefruit and/or pomelo for 7 days prior to dosing and during study period.
- Subjects will remain seated for the first 4 hours following drug administration, avoiding both vigorous exertion and complete rest. However, should adverse events occur at any time, subjects may be placed in an appropriate position. Subjects will not engage in strenuous activity at any time during the confinement.
- Female volunteers of childbearing potential will have to take appropriate measures to prevent pregnancy for at least 28 days prior to the administration of the study drug, during the study and for at least 60 days after the drug administration, as described in [Section 4.2](#).
- Male subjects who are apt to procreate will be expected to use an acceptable contraceptive regimen from day 1 of this study, throughout the duration of the entire study, and until at least 3 months after the drug administration, as described in [Section 4.2](#). Condoms with spermicide will be provided to subjects upon departure from the clinical site. In addition to the use of condoms with spermicide, subjects will be informed that it is strongly recommended that their female partner uses one of the two methods listed below:
 - Systemic contraceptives (birth control pills, injectable/ implantable/ insertable hormonal birth control products, transdermal patch).
 - Intrauterine device.
- Male subjects must refrain from sperm donation from the screening and until at least 3 months after the drug administration.

6. STUDY PROCEDURES AND GUIDELINES

Unless otherwise stated in this protocol, clinical site standard operating procedures (SOPs), which are available for all activities relevant to the quality of the study, will be followed during this study. The different parts of this study are summarized in [Table 2](#) and explained in the following sections. The list of assessments for each study part is indicated with an "X" when the

Research Protocol N° CUD-P9-453

Sponsor Project N° COL MIG-114

assessments have to be performed. Any deviation from protocol should be noted in the Case Report Forms (CRFs) and the Sponsor should be notified.

Table 2. Schedule of Assessments for All Subjects

Examination	Screening	Days			Post-Study Tests or ET ^a	End of Study
	Day 28 to -1	-1	1	2	2	7 (±3)
Review Inc/Exclusion Criteria & MedicalHistory	X					
Informed Consent	X					
Check-in		X				
Dosing			X			
Clinic Confinement		X	X	X		
Discharge				X		
Demographics	X					
C-SSRS questionnaire	X				X	
Concomitant Medication	X	X	X	X	X	X
Physical Examination	X				X	
Vital Signs ^b	X		X		X	
Height, Weight, and BMI	X					
12-lead ECG ^c	X		X		X	
HIV Ag/Ab Combo, HBsAg (B) (Hepatitis B) and HCV (C) Tests	X					
Drug and Alcohol Screen	X	X				
Pregnancy test (females)	X	X			X	
Clinical Laboratory Evaluations ^d	X	X			X	
PK Blood Sample ^e			X	X		
Follow-up Call						X
Adverse Events Recording	X	X	X	X	X	X

Research Protocol N° CUD-P9-453

Sponsor Project N° COL MIG-114

^a Early Termination (ET).

^b Vital signs will be measured prior to dosing and approximately 2 and 4 hours after study drug administration, including orthostatic blood pressure.

^c 12-lead ECG will be performed prior to dosing and approximately 2 hours after study drug administration.

^d Clinical laboratory tests (hematology, biochemistry, coagulation (screening only), endocrinology (screening only) and urinalysis) will be performed. On Day -1, these will be done in the evening prior to drug administration.

^e PK blood samples will be collected according to schedule of PK assessments in [Table 3](#).

Table 3. Schedule of Pharmacokinetic Assessments

PK Blood Sampling

Prior to dosing

0.25, 0.5, 0.75, 1, 1.25, 1.5, 1.75, 2, 2.5, 3, 4, 6, 8, 12, 16, 24 and
36 hours postdose

Time of PK sampling and dosing must be recorded.

6.1. Study Procedures

Safety assessments will include physical examination, vital signs (blood pressure, heart rate, and body temperature), 12-lead ECG, laboratory tests (hematology, biochemistry, and urinalysis), and continuous adverse event (AE) monitoring. Body weight and height will be measured at Screening and BMI will be calculated.

Clinically significant physical examination findings prior to the administration of study drug will be recorded as a medical history; clinically significant findings after the drug administration will be recorded as an AE.

The laboratory tests will be carried out according to the standard operating procedures of the licensed medical laboratory. Abnormal results will be verified to rule out laboratory error. Persistent relevant abnormal values should be followed up until the cause is determined or until the values return to the pre-medication value.

After the ICF is signed, information about all local and systemic clinical events, whether volunteered by the subject, discovered by Investigator questioning, or detected through other means, will be collected, recorded and followed as appropriate.

6.1.1. Physical Examination

A complete physical examination will be performed by a medically qualified and licensed individual as scheduled in [Table 2](#). The physical examination will include a review of the following: head and neck, heart, lungs, abdomen and general appearance.

Demographic data (age, gender, race, body weight adjusted for indoor clothing, height, BMI), and alcohol and smoking habits will be recorded.

During study days not requiring a complete physical examination, a symptom-targeted physical exam should be done if a new AE is reported, if medically indicated.

6.1.2. C-SSRS Questionnaire

A Columbia Suicide Severity Rating Scale will be performed as scheduled in Table 2.

6.1.3. Vital Signs

Vital sign measurements (body temperature, pulse rate, blood pressure and orthostatic blood pressure) are specified in Table 2. Vital signs can also be monitored during the study when judged necessary by the physician in charge or designee. Vital signs are to be performed prior to blood draws.

6.1.4. Laboratory Evaluations

Laboratory evaluations will be performed as scheduled in Table 2. The physician in charge or designee will assess each abnormal value to determine if it is clinically significant. Postdose clinically significant laboratory values will be reported as adverse events.

- General biochemistry: Sodium, potassium, chloride, glucose, blood urea nitrogen (BUN), creatinine, ClCr, eGFR, total bilirubin, alkaline phosphatase, uric acid (screening only), AST, ALT and albumin
- Hematology: White cell count with differential (absolute values of neutrophil, lymphocyte, monocyte, eosinophil, and basophil), red cell count, hemoglobin, hemoglobin A1c, hematocrit, mean corpuscular volume (MCV), and platelets count
- Coagulation: PT/INR and PTT levels (screening only)
- Urinalysis: Color, appearance, specific gravity, pH, leukocyte, protein, glucose, ketones, bilirubin, blood, nitrite, urobilinogen. Microscopic examination will only be performed if the dipstick test is outside of the reference range for leukocyte, blood, nitrite or protein
- Endocrinology: Ferritin (screening only)
- Serology: HIV Ag/Ab Combo, HBsAg and HCV
- Drug Screen: Alcohol, amphetamines, barbiturates, cannabinoids (THC), cocaine, opiates and phencyclidine (PCP)

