10. Willingness to adhere to the protocol requirements as evidenced by the informed consent form (ICF) duly read, signed and dated by the volunteer

Subjects with Normal Hepatic Function:

11. Clinical laboratory values within the laboratory's stated normal range; if not within this range, these must be without any clinical significance
12. Have no clinically significant diseases captured in the medical history or evidence of clinically significant findings on physical examination and/or clinical laboratory evaluations (hematology, general biochemistry, endocrinology, electrocardiogram [ECG], and urinalysis)
13. Must match by gender, as well as to the pooled mean values for age (± 10 years) and weight ($\pm 20\%$) of subjects with hepatic impairment

Hepatic Impaired Subjects:

14. Considered clinically stable in the opinion of the Investigator
15. Presence of mild hepatic impairment (Child-Pugh Class A: 5-6 points) or moderate hepatic impairment (Child-Pugh Class B: 7-9 points) at screening ([Appendix A](#))

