7. ADVERSE EVENTS

7.1. Definitions

An AE is defined as any untoward medical occurrence in a subject administered a medicinal product and which does not necessarily have to have a causal relationship with this treatment. AEs occurring after the initiation of the treatment are referred to as treatment emergent adverse events (TEAEs). An AE can therefore be any unfavorable and unintended sign (for example, an abnormal laboratory finding), symptom, or disease temporally associated with the use of a medicinal product, whether or not considered related to this medicinal product.

A suspected adverse reaction is any adverse event for which there is a reasonable possibility that the drug caused the adverse event. ‘Reasonable possibility’ means there is evidence to suggest a causal relationship between the drug and the adverse event. A suspected adverse reaction implies a lesser degree of certainty about causality than adverse reaction, which means any adverse event caused by a drug.

An AE may be:

- A new illness,
- Worsening of a concomitant illness,
- An effect of the study medication; it could be an abnormal laboratory value as well as a significant shift from baseline within normal range which the Principal Investigator or medical qualified designate considers to be clinically important.

Surgical procedures themselves are not AEs. They are therapeutic measures for conditions that required surgery. The condition for which the surgery is required is an AE, if it occurs or is detected during the study period. Planned surgical measures permitted by the clinical study protocol and the conditions(s) leading to these measures are not AEs, if the condition(s) was (were) known before the start of study treatment. In the latter case, the condition should be reported as medical history.

A serious adverse event (SAE) or reaction is any untoward medical occurrence that at any dose:

- Results in death,
- Is life-threatening,
- Requires inpatient hospitalization or prolongation of existing hospitalization,
- Results in persistent or significant disability or incapacity (defined as a substantial disruption of a person's ability to conduct normal life functions),
- Is a congenital anomaly or birth defect,

Is an important medical event (including development of drug dependence or drug abuse) that may jeopardize the subject or may require intervention to prevent one of the other outcomes listed above (according to medical judgment of the Principal Investigator).

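### Sections 6.1 and 6.1.4 make post-dose findings adverse events by timing alone, so unchanged liver disease can be recorded as treatment-emergent in the impaired groups, contrary to the worsening wording in 7.1

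*Protocol*

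**What the plan says.** Four provisions of the protocol bear on this.

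- **Laboratory values (6.1.4).** "The physician in charge or designee will assess each abnormal value to determine if it is clinically significant". The next sentence is the recording rule: "Postdose clinically significant laboratory values will be reported as adverse events".
- **Physical findings (6.1).** "Clinically significant physical examination findings prior to the administration of study drug will be recorded as a medical history"; by contrast, "clinically significant findings after the drug administration will be recorded as an AE".
- **Definitions (7.1).** The list of what an adverse event may be includes "Worsening of a concomitant illness", alongside a new illness and an effect of the study medication. The treatment-emergent label is set by timing: "AEs occurring after the initiation of the treatment are referred to as treatment emergent adverse events (TEAEs").
- **Entry of controls (4.2, criterion 11).** "Clinical laboratory values within the laboratory's stated normal range; if not within this range, these must be without any clinical significance". Criterion 12 adds that controls have no clinically significant disease or examination finding. Subjects in Groups 1 and 2 must instead have Child-Pugh Class A or B disease (criterion 15).

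Section 8.3.1.1 summarises adverse events by group. The secondary objective (2.2) is safety and tolerability in the normal, mild and moderate groups.

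**The concern.** The rules that site staff follow when completing the case report form are broader than the protocol's own definition. Under 7.1 a pre-existing illness becomes an adverse event when it worsens. Under 6.1 and 6.1.4 a clinically significant finding becomes one because it was seen after the tablet was taken.

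In many trials this looseness would affect all arms alike. Here it cannot, because pre-existing liver abnormality is what separates the groups. Any unchanged finding recorded in this way falls on Groups 1 and 2 and would look like poorer tolerability with declining hepatic function. The three centers could also apply the rule differently, since the text does not say whether an unchanged but significant value counts.

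**Working it through.** The protocol gives no figure for this point, so there is none to reproduce. The check compares the texts and then asks how far group membership alone could trigger the rule.

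**1. What each rule asks**

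| Place | Must be clinically significant? | Must be after dosing? | Must be new or worse? |
|---|---|---|---|
| 6.1.4, laboratory values | Yes | Yes | Not stated |
| 6.1, physical findings | Yes | Yes | Not stated |
| 7.1, TEAE sentence | No | Yes | Not stated |
| 7.1, concomitant illness | No | No | Worsening |

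Section 6.1 does mention the pre-dose value, but only to say when follow-up may stop: "Persistent relevant abnormal values should be followed up until the cause is determined or until the values return to the pre-medication value". It is not used to decide whether a value is an adverse event.

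**2. What is looked at again after dosing.** Table 2 repeats the laboratory panel and the physical examination at the Day 2 post-study tests. Of the five Child-Pugh items in Appendix A, bilirubin and albumin are in the repeated panel (6.1.4), and the abdomen is examined (6.1.1), so ascites may be seen. INR is measured at screening only. Encephalopathy is not a listed component of the examination.

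**3. Does class membership guarantee an abnormal repeated item?** Five items scored 1 to 3 have a minimum total of 5. Counting all item combinations:

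- Class A (5 to 6 points): 6 combinations. In 4 of them bilirubin and albumin both score 1.
- Class B (7 to 9 points): 90 combinations. In 19 of them bilirubin and albumin both score 1. If ascites must also score 1, INR and encephalopathy have to total 4, 5 or 6, which can happen in 3 + 2 + 1 = 6 ways.
- Class B without the 3-point encephalopathy level (taking the exclusion of severe encephalopathy to remove it): 75 combinations. Of these, 13 have normal bilirubin and albumin, and 3 have normal ascites as well.

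These are counts of combinations, not patient frequencies. They show that every Class B subject has some abnormal item at entry, but not always one that is repeated after dosing.

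**4. Illustration of size.** Let p be the chance that an impaired subject has an unchanged abnormality that is judged clinically significant after dosing. The protocol gives no value, so p is an assumption. The expected number of such subjects among 8 + 8 = 16 is 16p. The chance of at least one in a group of 8, treating subjects as independent, is 1 − (1 − p)^8.

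| p (assumed) | Expected of 16 | At least one in a group of 8 |
|---|---|---|
| 0 | 0 | 0 |
| 0.10 | 1.6 | 0.57 |
| 0.25 | 4 | 0.90 |
| 0.50 | 8 | 0.996 |

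The corresponding number of carried-over findings in Group 3 is about zero, because criteria 11 and 12 apply the same clinical-significance test at entry. Controls can still have genuinely new events.

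**The case against.** The strongest reply is that the sections, read together, already give the right rule. An adverse event is defined as something that occurs, and an unchanged condition does not occur after dosing. Section 7.1 speaks of worsening and of a shift from baseline. Pre-dose physical findings go to medical history. A physician must first judge a value clinically significant, and impaired subjects must be clinically stable at entry (criterion 14). Pre- and post-dose values will be available, so a reviewer of up to 24 subjects can see what did not change. The statistical analysis plan may also refine how treatment-emergent events are tabulated.

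Much of this stands, and it limits the size of the problem. It does not remove the conflict. The physician is asked whether a value is significant, not whether it has changed. Recording a finding as history does not stop 6.1 from making the same finding an event later. Nothing says that 7.1 overrides 6.1 or 6.1.4. A tabulation rule also acts only after the site has made the entry.

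A reader might infer stronger conclusions, which the protocol does not support:

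- *That the liver disease will be counted as drug toxicity.* Treatment-emergent is a matter of timing. Table 5 assesses causality separately, and its related category requires that the subject's clinical state does not readily explain the event.
- *That all 8 moderate subjects and no control will carry such an event.* Eight of 8 is only a ceiling. It ignores physician judgement and the items that are not repeated.
- *That the review of the first four mild subjects will be distorted.* A Class A score of 5 needs no abnormal item, and no adverse event threshold is stated for that review.
- *That the protocol never refers to baseline.* Section 7.1 does. The gap lies in 6.1, 6.1.4 and the TEAE sentence.

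**Conclusion.** The point holds as a conflict between the site-level recording rules and the protocol's own definition. Followed as written, those rules allow an unchanged abnormality of the qualifying liver disease to be recorded as a TEAE, and the exposure is one-sided: possible in Groups 1 and 2, hardly in Group 3. The by-group safety summary could therefore be biased towards more events in impaired subjects. That it will be biased, and by how much, cannot be shown from the protocol. The conclusion assumes that at least some sites apply 6.1 and 6.1.4 literally and judge some unchanged values clinically significant. Because only the secondary safety objective is touched, this is a moderate wording problem, worth correcting because the correction is cheap.

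**What to change.** Reconcile 6.1, 6.1.4 and the TEAE sentence in 7.1 with the worsening wording already in 7.1. Suggested text: *A post-dose laboratory value or physical finding is an adverse event only if it is new, or has worsened to a clinically significant degree, compared with the last pre-dose assessment (Day -1 laboratory panel; screening physical examination). Unchanged findings remain in medical history.* Put the same condition in the TEAE sentence and in the case report form instructions.

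The cost is a few sentences. No new measurements are needed, since Table 2 already schedules both pre-dose assessments. The downside is that the investigator must compare each significant finding with baseline. For physical findings that baseline is the screening examination, which may precede dosing by some weeks.
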